3.2.1 Inclusion Criteria

- Inpatients and outpatients with kidney function (eGFR) allowing for safe administration of standard contrast dose (as calculated with the OmniVis calculator).
- Patients with clinical suspicion of disease of the aorta and/or arteries in the lower limb.
- Referral to CTA diagnosis, treatment planning or follow-up.

3.2.2 Exclusion Criteria

- Iodine contrast medium allergy
- Age < 18 years
- Lack of informed consent
- Critical ischemia of the lower extremities

3.3 Location

Akershus University Hospital, Department of diagnostic imaging.

3.4 CT Scanner and protocol

Scanner:

All patients: Philips Iqon Detector-based spectral CT (SDCT; Philips Healthcare, Cleveland, OH, USA)

Imaging protocols:

Randomized either to standard CTA or a dilution DL (dual layer) CTA examination. In the dilution examinations the amount of injected iodinated contrast medium will be reduced by means of a dilution technique. The dilution technique is efficient and safe since it allows the use of the standard injection protocol (flow rate, volume, iodine concentration, saline chaser) from conventional CT. We set a limit for the contrast injection speed to less than 7,0 ml/s. In order not to exceed this contrast flow rate limit, the maximum volume is limited to 130 ml. Minimum contrast volume is limited to 60 ml. The contrast injection is followed by a flush of 50ml saline at the same flow rate. Injection rate will be determined using formula:

Contrast medium volume (ml)/ Injection time

Injection Speed (ml/s) = -----

21s (CTA of lower limb)

The examination (study and controls) may be supplemented with a feet to hip scan after the main scan if there is suspicion of suboptimal examination quality.

All dual layer dilution examinations are checked by radiologist before the patient leaves the lab.

IQon Spectral CT	CTA of lower limb K+
Patient related parameters	
Contrast concentration, mg I/ml	350
Volume iodine contrast medium, ml	Control group: 1.Bolus:1,4ml/kg max 130ml. 2.Bolus: 50ml NaCl Study group: 1.Bolus:70%NaCl and 30%iodine 2.Bolus: 50ml NaCl Injection time:21s
Technical related parameters	
Flow rate, ml/s	Adjust to achieve desired injection
Trigging threshold, HU	120
Post threshold delay, s	15
NaCl	50ml

Scan parameters	CTA lower extremities
kV	120
Scan	Helical
Scan type	CTA Carotid
Slice Thickness	0,9mm

Increment	0,45mm
Collimation	Auto
Average mAs	228
Min/max mAs	70/200
DRI	27
Dose right	3D
Pitch	1,171
Rotation time	0,5
Resolution	Standard
iDose	4?
IMR	Routine level 1
MonoE40	Spectral 3
MonoE45?	Spectral 3
CTDIw	20,6mGy

3.5 Patient data and Measurements:

3.5.1 Patient data / Variables:

Demographics: Age, gender, weight, height, BMI.

Medical parameters: Creatinine, eGFR.

Comorbidities: Diabetes, cardiovascular disease

Contrast medium: Iodine contrast medium concentration/volume, iodine injection flow rate.

3.5.2 Objective examination quality analysis:

From each imaging examination from the iQon a total of three datasets of vni at 40, 50 keV levels, and conventional, will be reconstructed with spectral 3 level. Conventional images from the control group are compared to vni at 40 and 50 keV in the study group.

For study and control examinations arterial attenuation, image noise, Signal to Noise Ratio (SNR) and Contrast to Noise Ratio (CNR) is recorded.

Arterial attenuation is measured by an experienced radiology technician (where appropriate) in the:

- Abdominal aorta (at the midpoint between the renal arteries and the aortic bifurcation)
- Iliaca communis (at the midpoint between the aortic bifurcation and iliac bifurcation)
- Femoralis superficialis (ca 10 cm inferior to the branching of the deep femoral artery)
- Poplitea (p3 – inferior part of a. Poplitea).

The measurements are performed by placing a region of interest (ROI) within the artery at predefined levels.

Image noise is measured by placing a ROI in air and measuring the standard deviation of the attenuation.

Signal to Noise Ratio (SNR) is measured by dividing the mean arterial attenuation (at defined levels) by mean image noise.

Contrast to Noise Ratio (CNR) is measured by dividing the difference between arterial and muscular attenuation by the image noise: (arterial attenuation - muscular attenuation) / Image noise

Vascular pathology is classified according to the TASC II grading system by an interventional radiologist.

Pas id: nummer – (0=standard, 1=studie, a = keV40, b=keV50)

3.5.3 Subjective /semiquantitative assessment of examination quality:

Subjective examination quality will be rated on a 4-point scale separately by 2 interventional radiologists who are blinded to each other's rating. Discrepancies will be resolved by a third rater.

The subjective rating is performed at the same anatomical levels as the objective measurements. Additionally subjective examination quality is rated in the calf as the best of the three arteries: a. tibialis post., a. tibialis ant. eller a. fibularis.

The rating is performed separately on the left and right side and on conventional, MonoE 40 keV and MonoE 50 keV.

Images that cannot be assessed due to metal artifacts such as hip replacements are labelled "missing" - 9.

Rating	Definition
1	Excellent: The demarcation of the vessel lumen is excellent, more than sufficient for confident diagnosis or exclusion of stenosis or occlusion.
2	Good: The demarcation of the vessel lumen is sufficient for confident diagnosis or exclusion of stenosis or occlusion.
3	Adequate: The demarcation of the vessel lumen is adequate for diagnosis or exclusion of stenosis or occlusion but with limited confidence.
4	Non-diagnostic: There is insufficient demarcation of the vessel lumen for diagnosis or exclusion of stenosis or occlusion.
8	Thrombosis or occlusion at this anatomic level. Enhancement cannot be assessed
9	Missing

3.6 End points:

3.6.1 Primary endpoint:

Mean attenuation in the aorta, common and external iliac artery, femoral artery.

3.6.2 Secondary endpoints:

Rate of diagnostic quality angiography (defined as arterial enhancement > 200 HU)

Subjective examination quality

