1.5 This study

We plan to perform a randomized controlled trial for CT examinations of the abdominal aorta and lower extremities. In this RCT, a new ultra-low iodine contrast medium examination procedure tailored for spectral CT on the Philips iQon is compared to the standard examinations.

2 Objectives:

The objectives of this study are:

Evaluation of ultra-low iodine load CTA protocols of the aorta and lower extremities.

To investigate whether dual-layer in combination with virtual monoenergetic imaging (VNI) allows for reduction of contrast medium (CM) in CTA of the aorta and lower limbs with sustained objective and subjective examination quality parameters.

3 Materials and Methods:

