3.2 Population, Sample size and Recruitment (Inclusion & exclusion)

In-patients and outpatients at AHUS.

Sample size: alfa (level of significance): 0.05, beta (power) 80%. Assuming a mean difference of 0.5 points (on the subjective 5-point scale) with a standard deviation between 1 and 1.5 results in a sample size of 100 in each group.

With SD = 0.8 sample size is 50 in each group.

With SD = 1 sample size is 63 in each group.

Med SD 1.5 sample size is 141 in each group.

Estimated inclusion time: 2 years.

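### No masking to arm is stated for the image readers or the third rater, so the subjective quality rating is open to reader bias; the primary attenuation endpoint is little exposed

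*Combined protocol and SAP*

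**What the plan says.** - **Readers (3.5.3).** Quality is rated "separately by 2 interventional radiologists who are blinded to each other's rating", and a third rater settles discrepancies. This is the only masking described.
- **What is rated (3.5.3).** "The rating is performed separately on the left and right side and on conventional, MonoE 40 keV and MonoE 50 keV".
- **What is compared (3.5.2).** "Conventional images from the control group are compared to vni at 40 and 50 keV in the study group".
- **Dataset identifier (end of 3.5.2).** The code reads "0=standard, 1=studie, a = keV40, b=keV50", so it carries both arm and energy level.
- **On-table check (3.4).** A radiologist looks at every dilution examination before the patient goes. No such check is stated for controls.
- **Role of the rating.** Section 3.6.2 lists it as a secondary endpoint. The objective in Section 2 asks for less contrast medium "with sustained objective and subjective examination quality parameters", and the sample size in 3.2 rests on a 0.5-point difference in this rating.
- **Primary endpoint (3.6.1).** "Mean attenuation in the aorta, common and external iliac artery, femoral artery". A technician measures attenuation in regions of interest at set levels (3.5.2).

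**The concern.** The grades call for judgement. Excellent and good differ only in whether the lumen is shown more than well enough, or well enough, for a confident diagnosis. A reader who knows the arm can move a score by one grade for reasons unrelated to the image, and randomisation does not protect against that.

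Defined grades, two separate readers and a third rater limit the effect of one person's habits. They do not remove an expectation that all three share. Such a shift need not lower inter-observer agreement, so the agreement analysis in 3.7 may not show it.

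The direction cannot be predicted. Section 4.1 expects study images to match or surpass the standard, yet also allows for slightly more inconclusive scans. A shift could therefore create a difference that is not there, or hide a real one. Hiding one matters here because the aim is to show that quality is sustained.

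**Working it through.** **1. Masking, role by role**

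| Role | Task | Masking stated |
|---|---|---|
| Two radiologists (3.5.3) | Grade each site, side and reconstruction | To each other's rating; nothing on arm |
| Third rater (3.5.3) | Resolves discrepancies | None |
| Technician (3.5.2) | Measures attenuation at set levels | None |

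Section 3.1 describes allocation by numbered envelopes and does not say from whom the result is kept. Section 4.2 promises de-identification, which protects privacy; a de-identified dataset can still carry an arm code.

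The documents contain two possible routes of unmasking: the identifier in 3.5.2 and the check of dilution examinations in 3.4. Neither is shown to reach the readers. The plan does not say that the identifier is displayed at reading, or that the checking radiologist is also a reader.

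The text before Section 1.1, and the text between Section 4.3 and reference 7, were not available. The statement that masking is absent covers the rest.

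**2. The plan's own sample size (3.2)**

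Inputs from 3.2: difference 0.5, alpha 0.05 (taken as two-sided), power 80%.

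n per group = 2 × (1.960 + 0.842)² × SD² / 0.5² ≈ 62.8 × SD²

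- SD 1: 62.8, so 63 (stated 63).
- SD 1.5: 141.3, so 142 rounding up (stated 141).
- SD 1.25, the midpoint of the stated range: 98.1, so 99 (the plan settles on 100).
- SD 0.8: 40.2, so 41 (stated 50). This figure does not reproduce, but nothing below depends on it.

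**3. What a shared reader shift would do**

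Assumptions: one score per patient, 100 per group, a two-sided 5% comparison of means (3.7 names no test), and a shift of 0.1 or 0.2 points. The documents give no shift. A shift of 0.1 or 0.2 corresponds to 10 or 20 of 100 patients in one arm being graded one step differently.

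SD 1 comes from 3.2, and SD 1.25 is the midpoint that supports 100 per group. SD 1.5 is not used. On grades 1 to 4, the largest common SD compatible with a 0.5-point difference is √(1.75 × 1.25) = 1.48.

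SE = SD × √(2/100)

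P(reject) = Φ(d/SE − 1.96) + Φ(−d/SE − 1.96), where d is the difference that the test sees.

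Worked case: SD 1, no true difference, shift 0.2. SE = 0.1414 and d/SE = 1.414, so P = Φ(−0.546) + Φ(−3.374) = 0.293.

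| Situation | d | SD 1 (SE 0.1414) | SD 1.25 (SE 0.1768) |
|---|---|---|---|
| No true difference, no shift | 0 | 0.050 | 0.050 |
| No true difference, shift 0.1 | 0.1 | 0.109 | 0.087 |
| No true difference, shift 0.2 | 0.2 | 0.293 | 0.205 |
| True difference 0.5, no shift | 0.5 | 0.942 | 0.807 |
| True difference 0.5, opposite shift 0.1 | 0.4 | 0.807 | 0.619 |
| True difference 0.5, opposite shift 0.2 | 0.3 | 0.564 | 0.396 |

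A simulation on whole grades 1 to 4, with base SD 1.01 and 10% or 20% of one arm moved by one grade, gave false-positive rates of 10.6% and 27.8%. These are close to the SD 1 column.

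**The case against.** **Masking may achieve little.** In the planned comparison, control conventional images are set against study 40 and 50 keV images, so arm goes with reconstruction type. The study bolus is 30% contrast medium and 70% saline, so brightness may also hint at arm. This stands: recoding removes labels, not visual cues, and how much bias it would remove is not known. But all three reconstructions of every examination are rated, so reconstruction type alone does not identify arm. A label gives certainty where appearance gives only a hint.

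**The magnitude is assumed.** This also stands. The figures suppose that the whole shift survives two readings and third-rater resolution, and that each patient has one score. The plan rates by site, side and reconstruction and specifies no aggregation. The table shows sensitivity to a shift; it does not forecast one.

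**Stronger readings that a reader might infer.**
- *The identifier shows that readers see the arm.* The documents do not support this. The code stands at the end of the section on objective measurements, has no symbol for conventional images, and may serve data entry only.
- *The primary endpoint is compromised.* It is a measured value at predefined levels. Region placement is not stated to be masked, but the scope for expectation is small, and no effect on it is estimated.
- *The inflation is larger still at SD 0.8 with 100 per group.* Section 3.2 bases 100 per group on an SD of 1 to 1.5, and pairs the smaller SD with another size: "With SD = 0.8 sample size is 50 in each group".

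**Conclusion.** The gap is real and limited in scope. As written, the plan masks the readers only to each other and states no masking to arm for them or for the third rater. That leaves the subjective rating, on which the sample size rests, open to a bias that randomisation does not remove and the agreement analysis may miss.

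Under the stated assumptions, a shared shift of 0.1 to 0.2 points would roughly double the false-positive rate or take it to nearly six times its nominal level at SD 1. At SD 1.25 the effect on false positives is smaller, while the percentage-point loss of power is larger. Whether any shift would occur, and in which direction, cannot be known from the documents. Masking may also be intended in practice and simply not written down. The change is worth making because it costs little, not because bias has been shown.

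**What to change.** 1. Label the reading datasets with random codes that carry no arm or keV information, and hold the key outside the reading team.
2. Present both arms and all three reconstructions in random order.
3. State in 3.5.3 that the readers and the third rater are masked to arm. Add the technician in 3.5.2, which costs nothing more.
4. Where existing staffing allows, examinations should not be rated by the radiologist who did the on-table check in 3.4. Otherwise record the overlap. The check itself is not in question.
5. Report as a limitation that masking is partial, because image appearance may hint at arm and the planned comparison ties arm to reconstruction type.

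**Cost:** a recoding list, a shuffled reading order and a key holder. No extra scans, readers or patients are needed, and the sample size does not change.

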1.4 Spectral CT

The recently introduced spectral CT technique utilizes x-rays covering a spectrum of energy-levels as opposed to conventional CT in which x-rays are set to one specific energy level. Spectral Detector CT (SDCT) utilises a single X-ray tube but has two layers of detectors to simultaneously collect low and high energy data in all patients.

This technology offers many possibilities, such as “boosting” the x-ray contrast effect of iodine. This improves the vascular enhancement of the contrast medium using low-energy, virtual monoenergetic imaging (VNI).

Akershus University Hospital has recently acquired the first spectral CT scanner in Norway, the Philips iQon.

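### The primary endpoint names the external iliac artery, for which no measurement is planned, and the 40 and 50 keV comparisons are not ranked

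*Combined protocol and SAP*

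**What the plan says.** The primary endpoint in section 3.6.1 is one line: "Mean attenuation in the aorta, common and external iliac artery, femoral artery". It does not say how arteries or sides are combined, and it names no reconstruction.

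Section 3.5.2 gives the measurement plan. ROIs are placed at set levels in four arteries. The first is the abdominal aorta. The second is described as "Iliaca communis (at the midpoint between the aortic bifurcation and iliac bifurcation"). For the third, the plan gives the level as "Femoralis superficialis (ca 10 cm inferior to the branching of the deep femoral artery"). The fourth level, in the popliteal, is the "inferior part of a. Poplitea".

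On reconstructions, the same section says "Conventional images from the control group are compared to vni at 40 and 50 keV in the study group". The identifier scheme gives each level its own code: "a = keV40, b=keV50". The scan table in 3.4 lists MonoE40 and a queried MonoE45 entry, but no 50 keV entry.

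Section 3.7 plans a general comparison of subjective and objective quality between the groups. It names no test, artery, keV level, order of testing or multiplicity rule.

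**The concern.** Two things are left open in the quantity on which the trial will be judged.

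The first is what is averaged. An analyst who follows 3.5.2 will have no external iliac value to put into the 3.6.1 endpoint. Someone must then drop that artery, add a measurement, or use the popliteal in its place. These give different primary endpoints, and the plan does not choose among them.

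The second is which study-arm image is compared with control. Section 1.4 says of the spectral technique: "This improves the vascular enhancement of the contrast medium using low-energy, virtual monoenergetic imaging (VNI"). On that reasoning the 40 and 50 keV images can be expected to give different attenuation in the same patient, and the two comparisons with control may lead to different conclusions. With no primary comparison named, the one reported as primary could be chosen after both results are known.

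**Working it through.** **Step 1: the two artery lists side by side.**

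| Artery | In primary endpoint (3.6.1) | Has a planned ROI (3.5.2) |
|---|---|---|
| Aorta | yes | yes (abdominal) |
| Common iliac | yes | yes |
| External iliac | yes | **no** |
| Femoral | yes | yes, as superficial femoral |
| Popliteal | no | yes |

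Three of the four endpoint arteries have an ROI and one has none. The common iliac ROI cannot stand in for the external iliac: it is placed above the iliac bifurcation, where the external iliac begins.

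**Step 2: the number of primary comparisons.** Control conventional against study 40 keV, and control conventional against study 50 keV, make two. This assumes that arteries and sides are first combined into one mean. Without a combining rule, two is a minimum.

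**Step 3: the significance level.** The plan gives no figure for the primary endpoint in HU. Its only significance level is 0.05, in section 3.2, set for a 0.5-point difference on the subjective scale. Sidedness is not stated, but the plan's own sample sizes help. With n per group = 2(z_α + z_β)²SD²/0.5² and 80% power:

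- SD 1, two-sided: 2(1.960 + 0.842)² × 1/0.25 = 62.8, so 63. The plan says 63.
- SD 1, one-sided: 2(1.645 + 0.842)² × 1/0.25 = 49.5, so 50. This does not match.
- SD 1.25 (midpoint of the stated range, assumed), two-sided: 98.1, so 99. The plan says 100.
- SD 1.5, two-sided: 141.3, so 142. The plan says 141.

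Two-sided 0.05 is therefore a fair reading. The plan's 50 per group at SD 0.8 is not reproduced (41 two-sided), but nothing here depends on it.

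**Step 4: error rate if either keV level may count.** Let Z₄₀ and Z₅₀ be the two test statistics, standard normal with correlation ρ when there is no true difference at either level. Then

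P(at least one significant) = 1 − P(|Z₄₀| < 1.96 and |Z₅₀| < 1.96).

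The documents do not give ρ. It should be high, because both images come from the same scan and are compared with the same controls. The range below is an assumption.

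| ρ | P(neither significant) | P(at least one significant) |
|---|---|---|
| 0 (upper bound, for reference) | 0.95² = 0.9025 | 0.0975 |
| 0.8 | 0.9219 | 0.0781 |
| 0.9 | 0.9296 | 0.0704 |
| 0.95 | 0.9354 | 0.0646 |

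Counting only results that favour the study arm, the figures are 3.9% (ρ = 0.8) to 3.2% (ρ = 0.95), against 2.5% for a single test.

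**Step 5: sensitivity to the null assumption.** If 40 keV truly equals control and 50 keV truly lies one standard error lower, the chance of any favourable result is 2.5% for ρ from 0.8 to 0.95. The inflation in step 4 thus needs both levels to be close to no difference.

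**The case against.** The best reply is that this is a short protocol whose sections are meant to be read together, with 3.5.2 giving the working definition of a briefly worded endpoint. That answers the femoral point: 3.5.2 gives an exact superficial femoral level, so only the wording needs tidying. It does not answer the external iliac point, because 3.5.2 gives no level there to borrow.

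Four stronger readings are tempting, and the documents do not support them.

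- *The popliteal is measured for nothing.* It is absent only from the primary endpoint. Section 3.5.3 rates subjective quality at the same levels as the ROIs, and subjective quality is a secondary endpoint. The other secondary endpoint, "Rate of diagnostic quality angiography (defined as arterial enhancement > 200 HU"), names no artery and may include the popliteal. Measuring an artery outside the primary endpoint is not an error.
- *The queried 45 keV entry is a third candidate analysis.* Sections 3.5.2 and 3.5.3 use 40 and 50 keV throughout. The table entry looks like an unsettled scanner setting.
- *A split result, significant at 40 keV but not at 50 keV, would be an error.* If the levels truly differ, a split can be correct. The problem is only that the plan does not say which result decides.
- *The primary data are lost.* The external iliac lies between the common iliac and superficial femoral levels, both of which are measured, so an ROI can still be placed on the same images.

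It is also fair to say that step 4 is illustrative. It uses assumed correlations and a null at both levels, although section 1.4 suggests that the levels will differ. That limits the size of the inflation but does not supply the missing ranking.

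**Conclusion.** The point holds in two parts. The artery mismatch is wrong as written: sections 3.5.2 and 3.6.1 contradict each other, and the primary endpoint cannot be built from the planned measurements. This rests on the text alone. The unranked keV comparison is a gap that is cheap to close. Its size is about 6.5% to 7.8% against a nominal 5%, assuming two-sided tests, correlation 0.95 to 0.8, no true difference at either level, one combined mean attenuation per comparison, and either result being allowed to count. The plan does not say that either may count; it simply does not rule it out.

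Whether a non-significant difference could be read as sustained quality, and whether a margin in HU is needed, are separate questions and carry no weight here.

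**What to change.** Before analysis:

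1. Make the artery lists in 3.5.2 and 3.6.1 the same. Either delete the external iliac from the endpoint or add an external iliac ROI at a stated level. Write superficial femoral in the endpoint, and state that the popliteal is outside it if that is intended. State how arteries and the two sides are combined into one mean attenuation per patient, including when a segment cannot be measured.
2. Name one study-arm level, 40 or 50 keV, against control conventional as the primary comparison. Make the other secondary, or test it second in a fixed order. Bring the queried 45 keV entry in the 3.4 table into line with 3.5.2.

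The cost is protocol wording. If the external iliac is kept, add one more ROI per side on images already acquired. The sample size does not change, since naming one level or testing in a fixed order keeps the error rate at 0.05. The small downside is that one keV level loses primary status.
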